## ABBREVIATIONS

Abbreviations	Definitions
AE	Adverse event
CFR	Code of Federal Regulations
CRO	Contract Research Organization
CSR	Clinical study report
C trough	Trough concentration
CV	Coefficient of variation
ECG	Electrocardiogram
eCRF	Electronic Case Report Form
EOT	End of treatment
EOS	End of study
HDSM-Ax	Hyperhidrosis Disease Severity Measure-Axillary
HDSM-Ax, Child	Hyperhidrosis Disease Severity Measure-Axillary, Child
hr, h, hrs	Hour(s)
LC-MS/MS	Liquid chromatography with tandem mass spectrometry
MedDRA	Medical Dictionary for Regulatory Activities
mg	Milligram(s)
min	Minutes
mL	Milliliter(s)
N	number
PGI-S	Patient Global Impression of Severity
PGI-C	Patient Global Impression of Change
PK	Pharmacokinetics
PT	Preferred term
QD	Once daily
SAE	Serious adverse event
SAP	Statistical Analysis Plan
SD	Standard deviation
SRC	Study Review Committee
TEAE	Treatment-emergent adverse event
US	United States of America

## 1 REVISION HISTORY

Revision No./ Date	Author of Revision	Section(s) Modified	Description and/or Reason(s) for Revision

 Update the last revision dates on the cover page and the footer

 Provide first initial and last name

## 2 INTRODUCTION

### 2.1 Background

Sofspironium bromide (BBI-4000) is a novel soft-anticholinergic ester analog of glycopyrrolate in development for the topical treatment of primary axillary hyperhidrosis.

### 2.2 Rationale

The pediatric pharmacokinetic (PK) and safety study (BBI-4000-CL-105), that precedes this long-term safety extension study, is a short treatment duration (7 days [ $\pm 1$  day]) PK study. The purpose of this study is to collect additional safety and tolerability information on children and adolescents following once daily (QD) sofspironium bromide gel, 15% treatment for up to 24 weeks. Furthermore, subjects enrolled in Study BBI-4000-CL-105 may only begin to perceive improvement of symptoms near its conclusion. Therefore, subjects who complete Study BBI-4000-CL-105 will be allowed the opportunity to participate in this long-term extension study (i.e., 24 weeks of treatment) in which they may potentially experience additional clinical benefit from sofspironium bromide gel, 15%. The data collected will further inform enhance the pediatric safety and tolerability profile of the study drug.

This Statistical Analysis Plan (SAP) is based on the protocol for Study BBI-4000-CL-108, Version 0 (Original), dated 21 September 2018.

## 3 STUDY OUTLINE

This multicenter, open-label extension study will evaluate the long-term safety, tolerability, and PK of sofspironium bromide gel, 15%, when applied (QD) for up to 6 months in pediatric subjects  $\geq 9$  years to  $\leq 17$  years of age with axillary hyperhidrosis previously enrolled in Study BBI-4000-CL-105.

Following completion of the initial PK and safety study (Study BBI-4000-CL-105), subjects will be provided the opportunity to enter a 6-month open-label extension study. Subjects will be screened for eligibility at Day 8 of Study BBI-4000-CL-105 (last PK sample collection under BBI-4000-CL-105 study). Therefore, for participating subjects, the final treatment visit (i.e., Day 8/Visit 4) of Study BBI-4000-CL-105 and the Screening/Enrollment visit (i.e., Week 0 [Day 1]) of Study BBI-4000-CL-108 (long-term extension study) will take place simultaneously.

Subjects (parent/guardian) will be dispensed one container of sofspironium bromide gel, 15% each month at Visits 1-6. Subjects (and parent/guardian) will be instructed on the correct application procedure for sofspironium bromide gel, 15% (to be applied QD before bedtime to both axilla for up to 24 weeks).

[figure not shown]
Vital signs, review of concomitant medications, assessment of adverse events (AEs), completion of patient-reported outcomes (Hyperhidrosis Disease Severity Measure-Axillary [HDSM-Ax] and Hyperhidrosis Disease Severity Measure-Axillary, Child [HDSM-Ax, Child] and Patient Global Impression of Severity [PGI-S]), and urine pregnancy tests (UPT) for all females will be done each visit. Application site tolerability will be assessed at all visits through the end of treatment (EOT) at Week 24 (Day 168 [ $\pm 5$  days]). Blood and urine for safety testing will be collected and analyzed at Week 4 (Day 28 [ $\pm 3$  days]) and Week 24 (Day 168 [ $\pm 5$  days]) for routine hematology, chemistry, and urinalysis parameters. Electrocardiograms (ECGs) will be

assessed at Week 0 (pre-dose, Day 1), Week 4 (Day 28 [ $\pm 3$  days]), and Week 24 (Day 168 [ $\pm 5$  days]). A PK sample will also be collected at Week 4 (Day 28 [ $\pm 3$  days]) and at Week 24 (Day 168 [ $\pm 5$  days]). At Week 12 (Day [84  $\pm 5$  days]) and at the EOT at Week 24 (Day [168  $\pm 5$  days]), the subject will also complete the Patient Global Impression of Change (PGI-C). A final visit will be conducted 2 weeks after the last application of study drug. Clinically significant abnormal laboratory parameters and abnormal ECG noted at the previous visit, should be repeated at this visit. Comfort measures (e.g., topical analgesics and mechanical interference devices) may be used during all study blood collection events to reduce subject discomfort.

A total of 8 scheduled visits will take place over approximately 26 weeks: Week 0 (Day 1), Week 4 (Day 28 [ $\pm 3$  days]), Week 8 (Day 56 [ $\pm 5$  days]), Week 12 (Day 84 [ $\pm 5$  days]), Week 16 (Day 112 [ $\pm 5$  days]), Week 20 (Day 140 [ $\pm 5$  days]), Week 24 (Day 168 [ $\pm 5$  days]), and Week 26 (Day [182  $\pm 5$  days]). Subjects who prematurely discontinue study drug will complete the EOT (Week 24/Visit 7) visit.

An internal Study Review Committee (SRC), comprising the Sponsor Medical Monitor, Lead Investigator and Contract Research Organization (CRO) Medical Monitor, will facilitate the management and identification of potential safety concerns, and will assess whether revisions to the study protocol and/or consent are required, and will evaluate the overall progress of the study.

## Figure 1 Study Schematic

#### 4 SCHEDULE OF ACTIVITIES

Description With Protocol Reference	Screening/ Enrollment	Treatment					End of Treatment/Early Termination	End of Study
Week	Week 0	Week 4	Week 8	Week 12	Week 16	Week 20	Week 24	Week 26
Study Day ( $\pm$ days)/ Visit	Day 1/ Visit 1	Day 28 ( $\pm$ 3)/ Visit 2	Day 56 ( $\pm$ 5)/ Visit 3	Day 84 ( $\pm$ 5)/ Visit 4	Day 112 ( $\pm$ 5)/ Visit 5	Day 140 ( $\pm$ 5)/ Visit 6	Day 168 ( $\pm$ 5)/ Visit 7	Day 182 ( $\pm$ 5)/ Visit 8
Consent/Assent Refer to Section 6.1	X							
Inclusion/Exclusion criteria Refer to Sections 5.1 and 5.2	X							
Demographics Refer to Section 6.2	X a							
Height/Weight Refer to Section 6.5	X a							
Abbreviated Physical Examination Refer to Section 6.4	X b	X					X	X
Medical/Medication History Refer to Section 6.3	X b							
Vital Signs Refer to Section 6.7	X b	X	X	X	X	X	X	X
HDSM-Ax and HDSM-Ax, Child, Refer to Section 6.8	X a	X	X	X	X	X	X	X
PGI-S Refer to Section 6.10	X a,b	X	X	X	X	X	X	X
PGI-C Refer to Section 6.11				X			X	
Safety laboratory testing Refer to Section 6.12.4.2	X a,b	X					X	X d
Pregnancy testing (females only) Refer to Section 6.12.4.1	X b	X	X	X	X	X	X	
PK sampling Refer to Section 6.12.5	X b	X c					X c	

Description With Protocol Reference	Screening/ Enrollment	Treatment					End of Treatment/Early Termination	End of Study
Week	Week 0	Week 4	Week 8	Week 12	Week 16	Week 20	Week 24	Week 26
Study Day ( $\pm$ days)/ Visit	Day 1/ Visit 1	Day 28 ( $\pm$ 3)/ Visit 2	Day 56 ( $\pm$ 5)/ Visit 3	Day 84 ( $\pm$ 5)/ Visit 4	Day 112 ( $\pm$ 5)/ Visit 5	Day 140 ( $\pm$ 5)/ Visit 6	Day 168 ( $\pm$ 5)/ Visit 7	Day 182 ( $\pm$ 5)/ Visit 8
12-lead ECG Refer to Section 6.8	X b	X					X	X d
Concomitant Medications Refer to Section 6.13	X b	X	X	X	X	X	X	X
AE Assessment Refer to Section 10	X b	X	X	X	X	X	X	X
Application Site Tolerability Assessment Refer to Section 6.6	X b	X	X	X	X	X	X	
Dosing, Refer to Sections 8.4 and 8.5 and Study drug application and dosing diary card completion Refer to Appendix C								
Compliance Refer to Section 8.5	X b	X	X	X	X	X	X	
Study Drug Dispensing Refer to Section 8.3	X	X	X	X	X	X		

a Baseline data (prior to first dose) collected under Study BBI-4000-CL-105 will be carried over to the current study.

b Data collected at EOT (Day 8 [ $\pm$ 1 day]) under Study BBI-4000-CL-105 will be carried over to the current study.

c Collection  $\geq$ 12 hours from evening application of drug.

d Only collect if abnormal at Visit 7/Early Termination Visit.

## 5 STUDY DURATION

Each subject will participate in the study for up to 26 weeks:

- Screening (Day 1)
- Treatment (24 weeks)
- Follow-up (2 weeks after last dose)

 Subjects enrolled in Study BBI-4000-CL-105 opting to enroll in this extension study will continue receiving study drug in the extension study. The screening visit of Study BBI-4000-CL-108 (Visit 1 [Day 0]) and EOT visit of Study BBI-4000-CL-105 (Day 8 [ $\pm 1$  day]) will be conducted simultaneously.

## 6 STUDY POPULATON

Subjects enrolled in this study will be males and females,  $\geq 9$  to  $\leq 17$  years of age, with axillary hyperhidrosis who participated in and completed Study BBI-4000-CL-105.

## 7 STUDY OBJECTIVES AND ENDPOINTS

### 7.1 Objectives

#### 7.1.1 Primary Objectives

##### 7.1.1.1 Safety

To assess the long-term safety and tolerability of sofrironium bromide gel, 15% applied topically QD for up to 24 weeks in children and adolescent subjects,  $\geq 9$  to  $\leq 17$  years of age, with axillary hyperhidrosis.

##### 7.1.1.2 Pharmacokinetics

To assess the systemic exposure ( $C_{trough}$ ) of sofrironium and its primary metabolite (BBI-4010) following topical application of  $\sim 0.67$  mL of sofrironium bromide gel, 15% applied topically to each axilla, QD for up to 24 weeks.

#### 7.1.2 Exploratory Objectives

- To assess the effect of topically applied sofrironium bromide gel, 15% on HDSM-Ax and HDSM-Ax, Child in pediatric subjects,  $\geq 9$  to  $\leq 17$  years of age, with axillary hyperhidrosis
- To assess the effect of topically applied sofrironium bromide gel, 15% on Hyperhidrosis Disease Severity Measure-Axillary (HDSM-Ax) Summary Questions; duration (No. 4) and severity (No. 5) in pediatric subjects,  $\geq 9$  to  $\leq 17$  years of age, with axillary hyperhidrosis
- To assess the effect of topically applied sofrironium bromide gel, 15% on PGI-S in pediatric subjects,  $\geq 9$  to  $\leq 17$  years of age, with axillary hyperhidrosis
- To assess the effect of topically applied sofrironium bromide gel, 15% on PGI-C in pediatric subjects,  $\geq 9$  to  $\leq 17$  years of age, with axillary hyperhidrosis.

## 7.2 Endpoints

### 7.2.1 Primary Endpoints

#### 7.2.1.1 Safety

- Incidence and severity of application site burning, itching, stinging, scaling and erythema
- Incidence and severity of all AEs and their relationship to study drug
- Incidence of clinically meaningful change from baseline in safety laboratory parameters, physical examination, 12-lead ECGs and vital signs
- Proportion of subjects who discontinue treatment due to an AE

#### 7.2.1.2 Pharmacokinetics

- Determination of plasma concentrations ( $C_{trough}$ ) of sofrironium and BBI-4010 at Week 4 and Week 24 (EOT) following 24 weeks of QD topical application of sofrironium bromide gel, 15%.

### 7.2.2 Exploratory Endpoints

- Change of HDSM-Ax ( $\geq 12$  years of age) or HDSM-Ax, Child ( $\geq 9$  to  $< 12$  years of age) from baseline to EOT
- Change of HDSM-Ax Summary Questions; duration (No. 4) and severity (No. 5) from baseline to end of treatment.
- Change of PGI-S from baseline to EOT
- PGI-C at Week 12 (Day 84) and EOT

## 7.3 Study Assessments

### 7.3.1 Safety

- Adverse events at all visits
- Local application site tolerability assessments (including burning, itching, stinging, scaling and erythema) at all visits through Week 24 [Day 168] and Week 26 (Day 182), if applicable
- Vital signs (heart rate [HR], blood pressure, respiratory rate and temperature) at all visits through and including Week 26
- 12-lead ECG at Week 0 (Day 1), Week 4 (Day 28), Week 24 (Day 168), and Week 26 (Day 182), if applicable
- Laboratory testing (hematology, chemistry and urinalysis) at Week 0 (Day 1), Week 4 (Day 28), Week 24 (Day 168), and Week 26 (Day 182), if applicable
- Pregnancy test (females) at all visits through and including Week 26 (Day 182)

- Abbreviated physical examination at all visits through and including Week 26 (Day 182)

### 7.3.2 Pharmacokinetics

- Plasma samples will be collected  $\geq$ 12 hours after the last dose on Week 0 (Day 1) [per Day 8/Visit 4 of Study BBI-4000-CL-105], Week 4 (Day 28 [ $\pm$ 3 days]), and Week 24 (Day 168 [ $\pm$ 5 days]).

### 7.3.3 Efficacy

- HDSM-Ax or HDSM-Ax, Child as measured at all visits through and including Week 26 (Day 182 [ $\pm$ 5 days]).
- HDSM-Ax or HDSM-Ax, Child Summary Questions; duration (No. 4) and severity (No. 5) as assessed by the subject at all visits through and including Week 24 (Day 168)
- PGI-S, as measured by the subject at all visits through and including Week 26 (Day 182 [ $\pm$ 5 days]).
- PGI-C as measured by the subject at Week 12 (Day 112 [ $\pm$ 5 days]) and Week 24 (Day 168 [ $\pm$ 5 days]).

## 8 DOSING AND COMPLIANCE

All subjects will receive active study drug. One dose of sofrironium bromide gel, 15% will be applied topically using the supplied applicator to each axilla QD at approximately the same time before bedtime for up to 24 weeks. Sofpironium bromide gel is packaged in airless, multi-dose, metered pump containers. Each administration of sofrironium bromide gel, 15% is  $\sim$ 0.67 mL and contains 86.5 mg of sofrironium bromide, for a total daily dose when applied to both axillae of 173 mg.

The subject and/or the parent(s)/guardian(s) will record that the study drug was applied to each axilla (right and left) and when the subject applied the study drug in the dosing diary card. The site personnel will review the dosing diary card and weigh the pump container, with cap on, at Week 4 (Day 28 [ $\pm$ 3 days]), Week 8 (Day 56 [ $\pm$ 5 days]), Week 12 (Day 84 [ $\pm$ 5 days]), Week 16 (Day 112 [ $\pm$ 5 days]), Week 20 [Day 140 [ $\pm$ 5 days]), and Week 24 (Day 168 [ $\pm$ 5 days]).

## 9 BREAKING THE BLIND

Not applicable as this is an open-label study.

## 10 STUDY REVIEW COMMITTEE

An internal SRC, comprising the Sponsor Medical Monitor, Lead Investigator and CRO Medical Monitor, will facilitate the management and identification of potential safety concerns and will assess whether revisions to the study protocol and/or consent are required and will evaluate the overall progress of the study.

## 11 SAMPLE SIZE

Sample size is based on the planned enrollment under Study BBI-4000-CL-105. Up to 24 subjects may participate in this study.

## 12 GENERAL CONSIDERATIONS FOR DATA ANALYSIS

### 12.1 Analysis Populations

Two populations will be used for analysis: Safety and PK. The definition of these populations follows:

- **Safety Population:** All enrolled subjects who applied at least one dose of study drug and have at least one post-baseline safety assessment.
- **Pharmacokinetic Population:** All enrolled subjects who applied at least one dose of study drug and have at least one quantifiable PK sample for analysis.

### 12.2 Interim Analysis

No interim analyses are planned.

### 12.3 General Considerations for Analysis

#### 12.3.1 Safety and Efficacy Analysis

- The Safety population will be used for evaluation of safety and efficacy parameters.
- Analyses of safety and efficacy data will be performed in Statistical Analysis System (SAS) software version 9.2 or higher (SAS Institute Inc., 2008).
- The final analysis will be conducted after all subjects have completed the study and the database is locked. Listings will report all data collected in the database.
- If a data table is sparse, only a listing will be presented. Unless otherwise stated, all listings will be sorted by subject number and visit date. Continuous variables will generally be summarized using means, medians, standard deviation (SD), minimum, and maximum. Discrete variables will be summarized by frequency and percentages.
- Summary tables will indicate the number of subjects with complete data for each measurement, event, or outcome.
- Data will be summarized in plots organized by time point and over time.
- For multiple or repeated assessments for the same visit, the latest assessment will be included in the summary tables.
- Summary tables will only include data from scheduled visits.
- Data from unscheduled visits will be included in the listings.
- If additional analyses are required to supplement the planned analyses, they may be performed and will be identified in the appropriate section of the clinical study report

(CSR). Any substantial deviations from the planned SAP will be updated in the SAP and approved.

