### 13.3 Primary Analyses

#### 13.3.1 Safety

Safety evaluations will consist of AEs, application site local tolerability, physical examinations, vital signs, ECGs, and laboratory measurements (hematology, chemistry, and urinalysis).

- Adverse events:
  - Adverse events will be mapped to standard terms, i.e., MedDRA System Organ Class and Preferred Term.
  - Adverse events that occurred during the screening period will be listed separately and will not be included in the AE tabulations.
  - Adverse events that start on or after first dose will be considered a TEAE. At each post-baseline visit, the number and proportion of subjects reporting any given TEAE will be tabulated by severity; each subject will be counted only once according to the worst severity reported up to the current visit. Separate tables will be constructed for (a) all reported TEAEs, (b) protocol treatment related TEAEs, (c) serious TEAEs, and (d) TEAEs leading to protocol treatment discontinuation.
- At each applicable visit, local tolerability (burning, itching, stinging, scaling, and erythema at either axilla) will be described by severity as defined in Appendix E. Subject and Investigator assessments will be included in separate tables and listings, with the count and percentage of subjects within each severity (maximum severity assessed at either axilla) presented by parameter and visit.
- Vital signs will be summarized similarly as for laboratory parameters but without shift tables.
- Laboratory parameters will be descriptively summarized (mean, SD, median, minimum, maximum) for values at each visit and for changes from baseline at each subsequent visit. In addition, at each post baseline visit, parameter status (low, normal, high) will also be summarized as shift tables vs. baseline status.
- Descriptive statistics and/or frequency tables will be prepared as appropriate for physical examinations, and ECG (HR, QTcF, PR, and QRS) parameters, and abnormalities (e.g., normal; abnormal, not clinically significant; abnormal, clinically significant).
- Concomitant medications will be mapped according to the World Health Organization Drug Dictionary (WHODD) and will be presented in data listings.

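### Safety tables are limited to scheduled visits and laid out visit by visit, so none is defined to count subjects who ever had a laboratory, ECG or tolerability abnormality; the main exposure is a laboratory or ECG finding seen only at an unscheduled visit

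*SAP*

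**What the plan says.** Three rules in SAP 12.3.1 decide which values reach a summary table:

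- "Summary tables will only include data from scheduled visits".
- "Data from unscheduled visits will be included in the listings".
- "For multiple or repeated assessments for the same visit, the latest assessment will be included in the summary tables".

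The same section replaces a sparse table by a listing.

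Two primary safety endpoints in SAP 7.2.1.1 are worded as incidence: "Incidence of clinically meaningful change from baseline in safety laboratory parameters, physical examination, 12-lead ECGs and vital signs" and "Incidence and severity of application site burning, itching, stinging, scaling and erythema".

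SAP 13.3.1 sets out the tables. For laboratory tests, "at each post baseline visit, parameter status (low, normal, high) will also be summarized as shift tables vs. baseline status". For vital signs, "Vital signs will be summarized similarly as for laboratory parameters but without shift tables". For local tolerability, the output is the "count and percentage of subjects within each severity (maximum severity assessed at either axilla) presented by parameter and visit". ECGs get descriptive statistics or frequency tables, with no time basis stated. Adverse events are handled differently: each subject is counted once, at the worst severity reported so far.

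**The concern.** Incidence is a count of subjects who had the finding at least once. A set of by-visit tables does not give that count, and a rule that admits only scheduled visits can keep a subject out of every table.

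The protocol foresees data of this kind. Protocol 6.12.4.2 allows extra laboratory samples when clinically indicated, and Protocol 7.5 allows visits between the scheduled ones. An abnormality found only on such an occasion appears in a listing and nowhere else, unless it also becomes an adverse event. At stake is whether the reported incidence for a primary safety endpoint is the number of children ever affected or a smaller number.

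**Working it through.** The plan gives no figure to reproduce: the maximum of 24 subjects is carried over from the parent study (Protocol 11.1, SAP 11). The check is a reading of the plan, with simple arithmetic for size.

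**1. What each domain is planned to show**

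| Domain | Scheduled after Week 0 | Planned table | Count of subjects ever affected? |
|---|---|---|---|
| Laboratory | Weeks 4 and 24; Week 26 if abnormal at Week 24 | Summary and shift at each visit | No |
| ECG | Weeks 4 and 24; Week 26 if abnormal at Week 24 | Tables 14.3.5.2 to 14.3.5.4 | Not defined; Table 14.3.5.3 has incidence in its title but no time basis |
| Vital signs | Every visit to Week 26 | Summary at each visit, no shifts | No |
| Tolerability | Every visit to Week 24 | Severity by visit; Tables 14.3.4.5.3 to 14.3.4.5.7 | Not defined, although the titles mention incidence |
| Treatment-emergent AEs | By onset date | Worst severity to date | Yes |

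Even if Table 14.3.5.3 is meant as an any-time table, SAP 12.3.1 still limits it to scheduled visits.

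**2. Where an unscheduled value can arise.** Scheduled on-treatment laboratory tests and ECGs are 168 − 28 = 140 days apart. With the visit windows the gap runs from (168 − 5) − (28 + 3) = 132 to (168 + 5) − (28 − 3) = 148 days. The restriction is on visits, not on tests, so an extra sample taken at scheduled Visits 3 to 6 is not excluded. Week 26 repeats and early-termination assessments belong to scheduled visits and are tabulated. Unscheduled visits after Week 26 follow problems still present at Visit 8, so they mostly show persistence or resolution.

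**3. Whether the adverse event tables catch it.** Protocol 10.1 says that clinically significant changes in examinations, laboratory tests and vital signs may be recorded as adverse events; ECGs are not in that list. Protocol 10.2.1 generally keeps a laboratory abnormality out unless it needs intervention, comes with signs or symptoms, or leads to study termination or to treatment interruption or discontinuation. A finding outside these routes reaches only a listing.

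**4. By-visit counts without any unscheduled visit.** Suppose, as an illustration, that erythema is tabulated in one subject at each of the six visits from Week 4 to Week 24. That fits one subject affected throughout (1/24 = 4.2%) or six different subjects (6/24 = 25.0%). The by-visit severity counts are the same in both cases.

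**5. Size of one missed subject.** 1/24 = 4.2 percentage points at the maximum N. If fewer enrol (assumed values), 1/18 = 5.6 and 1/12 = 8.3. With exact 95% intervals, which the plan does not call for, 0/24 is 0% (0 to 14.2%) and 1/24 is 4.2% (0.1 to 21.1%).

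**The case against.** The strongest reply is that the gap is narrow and little is hidden. All data are listed, a separate listing of ECG abnormalities is planned (16.2.7.5), and 24 subjects can be counted by hand. Unscheduled visits between scheduled ones are for evaluating adverse events, so the triggering event should already be in the adverse event tables, and a laboratory abnormality that explains symptoms meets the Protocol 10.2.1 criterion. Protocol 6.6 likewise makes local reactions adverse events when they need therapy, interruption or discontinuation. What remains is mainly an asymptomatic abnormality needing no action, the kind least likely to be called clinically meaningful. SAP 12.3.1 also allows supplementary analyses in the study report.

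Most of this stands, and it is why the point is minor. It does not remove the point. A count made by hand from listings leaves open what is counted until the data have been seen, in an open-label study; a supplementary analysis has the same weakness. The tolerability example needs no unscheduled visit at all.

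A reader might infer more than the documents support:

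- That no any-time count exists anywhere. The treatment-emergent adverse event tables are cumulative at worst severity.
- That the latest-assessment rule will discard valid abnormal values. The only same-visit repeat foreseen is an ECG with artefact (Protocol 6.8), where the latest reading is the right one.
- That physical examinations have no summary. SAP 13.3.1 plans descriptive statistics or frequency tables for them, and Appendix A, which names only a listing, is preliminary.

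**Conclusion.** The point holds as a minor gap between endpoint and table. The plan names incidence as a primary safety endpoint but, outside adverse events, defines no table of subjects ever affected, and its scheduled-visit rule can leave out a laboratory or ECG abnormality. That laboratory tests and ECGs are the main exposure is an inference from their sparse schedule and the allowance for extra samples; the documents do not rank exposures.

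The undercount may be zero. The documents give neither an abnormality rate nor a rate of unscheduled testing, so a probability that the tables miss someone would only restate an assumed rate. What can be stated is 4.2 percentage points for each missed subject at N = 24. It would also go too far to say that the tables understate clinically meaningful change: that term is undefined, and no laboratory or vital-sign table of it is listed. The definition is a separate matter that this change does not settle. For the same reason no vital-sign row is proposed, since a subject count would need a threshold that the documents do not give.

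**What to change.** Keep the by-visit tables. Add to SAP 13.3.1 an any-time post-baseline row that uses all valid scheduled, repeat and unscheduled values after the SAP 12.4 baseline (so including the carried-over Week 0 value), and that excludes only readings documented as technically invalid:

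- **Laboratory:** number of subjects with any shift to low and, separately, any shift to high.
- **ECG:** define Table 14.3.5.3 as subjects with any out-of-range parameter at any post-baseline time, and add to Table 14.3.5.4 the number with any abnormal, clinically significant status.
- **Tolerability:** a maximum post-baseline severity row, either axilla, in Tables 14.3.4.5.3 to 14.3.4.5.7. Those titles list dryness where the endpoint lists stinging; this needs reconciling so that the row covers all five endpoint signs.

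State in SAP 12.3.1 that the scheduled-visit, latest-assessment and sparse-table rules do not apply to these rows.

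The cost is a short paragraph and a few extra rows from data already collected, with no change to study procedures. Protocol 11.3.1 lets the SAP be finalised up to database lock. The downside is that subjects with more assessments have more chances of an abnormal value, so the any-time figures may look slightly less favourable; a footnote can say so.
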